- a. Will email or telephone correspondence be used to screen potential subjects for eligibility prior to the potential subject coming to the research office? Xes \sum No
- b. If yes, identify below all health information to be collected as part of screening and check off any of the following HIPAA identifiers to be collected and retained by the research team during this screening process.

HEALTH INFORMATION TO BE COLLECTED:

A brief psychiatric and medical history will be collected during telephone screening including Axis I diagnoses, medical and neurologic diagnoses, as well as recent medication and psychotherapy

changes. All information will be stored in locked cabinets/password protected computer in an office that is locked. Information that will breach subject confidentiality will not be shared. Rather, data will only be released upon written consent of the subject and will be available for review by the Yale human Investigation Committee. We will hold paper files for seven years at which point they will be destroyed.

HIPAA identifiers:
Names ☐ Names ☐ All geographic subdivisions smaller than a State, including: street address, city, county, precinct, zip codes and their equivalent geocodes, except for the initial three digits of a zip code if, according to the current publicly-available data from
the Bureau of the Census: (1) the geographic unit formed by combining all zip codes with the same three initial digits contains
more than 20,000 people, and (2) the initial three digits of a zip code for all such geographic units containing 20,000 or fewer
people is changed to 000.
Telephone numbers
☐ Fax numbers ☐ E-mail addresses
Social Security numbers
Medical record numbers
Health plan beneficiary numbers
Account numbers
All elements of dates (except year) for dates related to an individual, including: birth date, admission date, discharge
date, date of death, all ages over 89 and all elements of dates (including year) indicative of such age, except that such ages
and elements may be aggregated into a single category of age 90 or older
☐ Certificate/license numbers
☐ Vehicle identifiers and serial numbers, including license plate numbers
Device identifiers and serial numbers
Web Universal Resource Locators (URLs)
Internet Protocol (IP) address numbers
Biometric identifiers, including finger and voice prints
Full face photographic images and any comparable images
Any other unique identifying numbers, characteristics, or codes
Assessment of Current Health Provider Relationship for HIPAA Consideration:
Does the Investigator or any member of the research team have a direct existing clinical
relationship with any potential subject?
Yes, all subjects
Yes, some of the subjects
∐ No
If yes, describe the nature of this relationship.
Subjects who have been seen in the clinic may be recruited. Some subjects may be referred for
psychopharmacology consult. Other subjects may come specifically because of interest in the study. No subjects
will be taken off current medication or withdrawn from ongoing therapy in order to participate in the trial,
unless the current medication is ineffective or causes unacceptable adverse effects. Patients who are not

5.

6. Request for waiver of HIPAA authorization: (When requesting a waiver of HIPAA Authorization for either the entire study, or for recruitment purposes only. Note: if you are collecting PHI as part of a phone or email screen, you must request a HIPAA waiver for recruitment purposes.)

interested in the study will be treated in the usual clinical manner.

	Choose one:
	☐ For entire study
	⊠ For recruitment purposes only
	☐ For inclusion of non-English speaking subject if short form is being used
	 Describe why it would be impracticable to obtain the subject's authorization for use/disclosure of this data;
	A waiver of HIPAA authorized is being requested for recruitment purposes only. Subjects will be initially recruited through word of mouth, TS advocacy organizations, physician referrals and internet ads. PHI such as name, telephone number and email addresses will be needed to schedule initial screening interviews. It would be impractical to coordinate initial subject enrollment and recruitment without this data.
	 ii. If requesting a waiver of signed authorization, describe why it would be impracticable to obtain the subject's signed authorization for use/disclosure of this data;
	Signed authorization is impractical, as the initial screening patients recruited through advertisements or referral may occur via phone or email.
	By signing this protocol application, the investigator assures that the protected health information for which a Waiver of Authorization has been requested will not be reused or disclosed to any person or entity other than those listed in this application, except as required by law, for authorized oversight of this research study, or as specifically approved for use in another study by an IRB.
	Researchers are reminded that unauthorized disclosures of PHI to individuals outside of the Yale HIPAA-Covered entity must be accounted for in the "accounting for disclosures log", by subject name, purpose, date, recipients, and a description of information provided. Logs are to be forwarded to the Deputy HIPAA Privacy Officer.
	 7. Required HIPAA Authorization: If the research involves the creation, use or disclosure of protected health information (PHI), separate subject authorization is required under the HIPAA Privacy Rule. Indicate which of the following forms are being provided: Compound Consent and Authorization form HIPAA Research Authorization Form
8.	Consent Personnel: List the names of all members of the research team who will be obtaining consent/assent.

Page **31** of **161**

[name], MS, [name], [name], and

[name], BS.

9. Process of Consent/Assent: Describe the setting and conditions under which consent/assent will be obtained, including parental permission or surrogate permission and the steps taken to ensure subjects' independent decision-making.

Investigators and/or research staff will obtain consent during the initial screening visit. During this visit, all aspects of the study will be discussed and the inclusion criteria will be explained.

10. Evaluation of Subject(s) Capacity to Provide Informed Consent/Assent: Indicate how the personnel obtaining consent will assess the potential subject's ability and capacity to consent to the research being proposed.

The consent documents will be reviewed verbally with the subject. If for any reason, it becomes clear that the subject cannot comprehend trial design or procedures, they will not be enrolled in the study.

11. Documentation of Consent/Assent: Specify the documents that will be used during the consent/assent process. Copies of all documents should be appended to the protocol, in the same format that they will be given to subjects.

Compound Authorization Form

12. Non-English Speaking Subjects: Explain provisions in place to ensure comprehension for research involving non-English speaking subjects. If enrollment of these subjects is anticipated, translated copies of all consent materials must be submitted for approval prior to use.

This protocol will not involve non-English speaking subjects.

12(a) As a limited alternative to the above requirement, will you use the short form* for
consenting process if you unexpectedly encounter a non-English speaking individual interested
in study participation and the translation of the long form is not possible prior to intended
enrollment?
YES □ NO □

Note* If more than 2 study participants are enrolled using a short form translated into the same language, then the full consent form should be translated into that language for use the next time a subject speaking that language is to be enrolled.

Several translated short form templates are found on our website at: http://www.yale.edu/hrpp/forms-templates/biomedical.html. If the translation of the short form is not available on our website, then the translated short form needs to be submitted to the IRB office for approval via amendment prior to enrolling the subject. *Please review the guidance and presentation on use of the short form available on the HRPP website.*

If using a short form without a translated HIPAA Research Authorization Form, please request a HIPAA waiver in the section above.

 13. Consent Waiver: In certain circumstances, the HIC may grant a waiver of signed consent, or a full waiver of consent, depending on the study. If you will request either a waiver of consent, or a waiver of signed consent for this study, complete the appropriate section below. Not Requesting a consent waiver Requesting a waiver of signed consent Requesting a full waiver of consent
A. Waiver of signed consent: (Verbal consent from subjects will be obtained. If PHI is collected, information in this section must match Section VII, Question 6) Requesting a waiver of signed consent for Recruitment/Screening only If requesting a waiver of signed consent, please address the following: a. Would the signed consent form be the only record linking the subject and the research?
Yes No No Does a breach of confidentiality constitute the principal risk to subjects? Yes No
OR
c. Does the research activity pose greater than minimal risk? Yes If you answered yes, stop. A waiver cannot be granted. Please note: Recruitment/screening is generally a minimal risk research activity No AND
d. Does the research include any activities that would require signed consent in a non-research context? Yes No
Requesting a waiver of signed consent for the Entire Study (Note that an information sheet may be required.) If requesting a waiver of signed consent, please address the following: a. Would the signed consent form be the only record linking the subject and the research? Yes No b. Does a breach of confidentiality constitute the principal risk to subjects? Yes No
OR
c. Does the research pose greater than minimal risk? Yes If you answered yes, stop. A waiver cannot be granted. No AND d. Does the research include any activities that would require signed consent in a non-research context? Yes No
B. Full waiver of consent: (No consent from subjects will be obtained for the activity.) Requesting a waiver of consent for Recruitment/Screening only

[F [b c	A. Does the research activity pose greater than minimal risk to subjects? Yes If you answered yes, stop. A waiver cannot be granted. Please note: Recruitment/screening is generally a minimal risk research activity No Will the waiver adversely affect subjects' rights and welfare? Yes No Why would the research be impracticable to conduct without the waiver? Where appropriate, how will pertinent information be returned to, or shared with subjects at a later date?
[Requesting a full waiver of consent for the Entire Study (Note: If PHI is collected, information here must match Section VII, question 6.)
I	f requesting a full waiver of consent, please address the following:
а [Г	A. Does the research pose greater than minimal risk to subjects? Yes If you answered yes, stop. A waiver cannot be granted. No
c d	b. Will the waiver adversely affect subjects' rights and welfare? Yes No be. Why would the research be impracticable to conduct without the waiver? H. Where appropriate, how will pertinent information be returned to, or shared with subjects at a later date?
	SECTION VIII: PROTECTION OF RESEARCH SUBJECTS
a. Wh about su F ii e li r	ality & Security of Data: nat protected health information (medical information along with the HIPAA identifiers) bjects will be collected and used for the research? Research staff will collect and use for research the following private identifiable information from subjects after consent is obtained: name, age, address, telephone number email address, diagnosis, results from the clinical evaluation, clinical rating scales aboratory tests (blood and urine), electrocardiogram (ECG) and physical examination results. Scientific reports will be written in aggregate terms. Individual responses will not be described if the data is published.
(ti b ii c	will the research data be collected, recorded and stored? Clinical data, outcomes of diagnostic instruments and research data will be collected by the principal investigator, co-investigators and study personnel. Collected information will be stored in a locked file cabinet in a locked office. Data will be entered by study personne nto a database, using a secured server, on a password protected computer in a locked office. Data may also be stored on an encrypted flash drive that will be stored in a locked office.
	wwww.www.www.www.www.www.www.www.www.w

d.	What methods and procedures will be used to safeguard the confidentiality and security of the identifiable study data and the storage media indicated above during and after the subject's
	participation in the study?
	Do all portable devices contain encryption software? X Yes No
	If no, see http://hipaa.yale.edu/guidance/policy.html
	All data will be coded and stored in locked cabinets on a password protected computer, a

All data will be coded and stored in locked cabinets on a password protected computer, as well as an encrypted flash drive, in a locked office. Private identifiable information about individuals will not be shared. A numbering code will be used to assign a unique identifier to each subject, that of which will be used for data entry stored on all secure electronic devices. Information that will breach subject confidentiality will only be released upon written consent of the subject and will be available for review by the Yale Human Investigation Committee. A Certificate of Confidentiality has been obtained.

e. What will be done with the data when the research is completed? Are there plans to destroy the identifiable data? If yes, describe how, by whom and when identifiers will be destroyed. If no, describe how the data and/or identifiers will be secured.

Paper files will be held for seven years after the completion of the study. After that point, all paper files will be destroyed. As noted previously, archived computer files will not have any identifying patient information.

f. Who will have access to the protected health information (such as the research sponsor, the investigator, the research staff, all research monitors, FDA, Yale Cancer Center Data and Safety Monitoring Committee (DSMC), SSC, etc.)? (please distinguish between PHI and de-identified data)

The principal investigator, co-investigators and all study personnel.

- g. If appropriate, has a Certificate of Confidentiality been obtained?
- h. *YES* Are any of the study procedures likely to yield information subject to mandatory reporting requirements? (e.g. HIV testing reporting of communicable diseases; parent interview -incidents of child abuse, elderly abuse, etc.). Please verify to whom such instances will need to be reported.

Yes. Evidence of abuse or situations in which the subject is deemed a danger to self or others will be reported.

SECTION IX: POTENTIAL BENEFITS

Potential Benefits: Identify any benefits that may be reasonably expected to result from the research, either to the subject(s) or to society at large. (Payment of subjects is not considered a benefit in this context of the risk benefit assessment.)

Subjects may benefit from the medical and psychiatric evaluations that they will receive while participating in the study. Patients will receive a higher level of evaluation and care than routine treatment.

SECTION X: RESEARCH ALTERNATIVES AND ECONOMIC CONSIDERATIONS

1. **Alternatives:** What other alternatives are available to the study subjects outside of the research?

Subjects may continue any current mediations or therapy, those of which might include various antipsychotics or alpha-2 antagonists, as well as habit reversal therapy. All of these interventions have demonstrated efficacy for the treatment of TS. Subjects will be presented with the risks and benefits of each of the treatments. Additionally, subjects will be offered any of the previously stated treatments that they have not received prior to enrolling in the trial.

2. **Payments for Participation (Economic Considerations):** Describe any payments that will be made to subjects, the amount and schedule of payments, and the conditions for receiving this compensation.

Participants may be paid up to \$650 total as compensation for participating in this study. They will receive a stipend payment of \$80 for the in-person screening assessment, \$70 for the Baseline, Week 4, Week 8, and Week 12 assessments; and \$35 for the Week 1, Week 2, Week 6 and Week 10 assessments. Additionally, They will receive a stipend payment of \$25 for each clinical follow-up assessment that you complete. Follow-up assessments will take place every 4 weeks for 6 months, after the end of the initial 12-week trial. Participants will receive such payments only for those visits that are completed.

If the participant travels more than 50 miles each way in order to participate in the study, they also may receive reimbursement for reasonable lodging and travel expenses in addition to the stipend outlined above, up to a total of \$200.00 per visit. Participants will need to provide receipts of your costs to the study coordinator.

According to the rules of the Internal Revenue Service (IRS), payments that are made to research subjects as a result of their participation in a study may be considered taxable income.

3. **Costs for Participation (Economic Considerations):** Clearly describe the subject's costs associated with participation in the research, and the interventions or procedures of the study that will be provided at no cost to subjects.

Subjects will not be charged for the study medications, clinical assessments, services or laboratory tests directly related to the study. As previously noted, some subjects may be seen for a clinical consultation at the Yale Child Study Center TS/OCD Clinic piror to study entry. Clinical consultation will be charged as part of care in the usual manner.

- 4. **In Case of Injury:** This section is required for any research involving more than minimal risk.
 - a. Will medical treatment be available if research-related injury occurs? Yes
 - b. Where and from whom may treatment be obtained?

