Subjects will be titrated up on Dronabinol dose during the first week of the trial (2.5mg Dronabinol for 3 days and then 5mg Dronabinol for 4 days increasing to 10mg Dronabinol for the remainder of the trial). Dronabinol will only be increased to 10mg at the week 1 assessment if the subject is tolerating the 5mg dose of Dronabinol and the Dronabinol may be reduced based on patient side-effects. Subjects will be assigned to receive two 400mg tablets of PEA daily for all 12 weeks. See pages 9-12 of this application for a detailed description of previous human use, known risks, and data addressing dosage(s), interval(s), route(s) of administration, and any other factors that might influence risks for both Dronabinol and PEA.

Assessments

Pre-study screening procedure: After an initial phone screen to rule out obvious exclusions from the study protocol, potential subjects will have an initial evaluation that will be performed by a multidisciplinary clinical team. In addition to a standard clinical evaluation consisting of history, and mental status exam, subjects will receive a clinical diagnostic interview using the Structured Clinical Interview of DSM-IV (SCID). Additional rating scales will assess severity of tic symptoms and common comorbid symptoms such as OCD, ADHD, depression and anxiety severity which are listed below.

Baseline Assessments	Medical Assessments	Rating scales
SCID	Vital Signs, ECG	YGTSS PUTS
Psychiatric History	Physical Exam	Y-BOCS Connors
General Medical History	Mental Status Exam	HAM-D HAM-A
Chart review of Med Hx	Baseline Labs	CGI AERS
	Urine Tox and Preg.	TSSL

Outcome Measures:

- Improvement in Tic Severity -- Yale Global Tic Severity Scale (YGTSS) (Total Tic Score)
- Improvement of Premonitory Urges -- Premonitory Urge for Tics Scale (PUTS)
- Self-Report of Tic Severity Tourette Syndrome Symptom List (TSSL)
- OCD Severity -- Yale-Brown Obsessive-Compulsive Scale (Y-BOCS)
- ADHD severity -- Connors Adult Attention Deficit Hyperactivity Rating Scale (Connors)
- Depression Severity-- Hamilton Rating Scale for Depression (HAM-D)
- Anxiety Severity -- Hamilton Rating Scale for Anxiety (HAM-A)
- Overall Improvement -- Clinical Global Improvement Scale (CGI)
- Adverse Effects -- Adverse Events Rating Scale (AERS)

Safety Assessments:

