The subject population will include adults with significant tic symptoms that have not previously responded to evidence-based treatments for TS. Subjects will include interested patients from the TS/OCD clinic, as well as eligible subjects who respond to the clinicaltrials.gov website posting. Additionally, subjects will be recruited via email blast through local TS chapters and by contacting local providers who treat adults with TS. Furthermore, contact will be made with adult subjects who have recently completed other treatment trials for TS at the clinic and agreed to be contacted for future trials.

6. Subject classification: Ch	ieck off all classificat	tions of subjects that will be specifically
recruited for enrollment i	n the research project	t. Will subjects who may require additional
•		in the study? If so, identify the population of ide a justification for their involvement.
☐ Children ☐ Non-English Speaking ☐ Decisionally Impaired ☐ Yale Students	☐ Healthy ☐ Prisoners ☐ Employees ☐ Females of child	Fetal material, placenta, or dead fetus Economically disadvantaged persons Pregnant women and/or fetuses bearing potential
* *		Il children who are wards of the state as tructions section VII #4 for further

7. **Inclusion/Exclusion Criteria:** What are the criteria used to determine subject inclusion or exclusion?

Inclusion Criteria:

- Adult between 18-60 years of age
- Meet DSM-5 criteria for the diagnosis of Tourette syndrome
- Significant current tic symptoms: YGTSS total tic score greater than or equal to 22 at baseline
- On stable psychiatric medication regimen for a minimum of 4 weeks prior to beginning the trial
- Accepted method of birth control

Exclusion Criteria:

- Comorbid bipolar disorder, psychotic disorder, substance use disorder, developmental disorder or intellectual disability (IQ<70)
- Recent change (less than 4 weeks) in other medications that have potential effects on tic severity (such as alpha-2 agonists (guanfacine, clonidine or prazosin), SSRIs, clomipramine, naltrexone, lithium, anxiolytics, topiramate, baclofen etc.). Medication change is defined to include dose changes or medication discontinuation.
- Recent change in behavioral treatment for Tourette syndrome or comorbid conditions (i.e. OCD) within the last 4 weeks or initiation of behavioral therapy for tics within the last 12 weeks.

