- Taking any co-medications (over the counter or prescription), food supplements/additives which can have a drug interaction with dronabinol or PEA.
- Positive pregnancy test or drug screening test
- History of cannabis dependence
- Significant Medical Comorbidity
- History of hypersensitivity to any cannabinoid or sesame oil

8. How will **eligibility** be determined, and by whom?

Subjects will first undergo a phone screen to initially determine eligibility. Information collected during the phone screen will be used only in the event that the subject continues to participate in the study.

After determining initial eligibility, research staff will provide a brief description of the research and the subject will undergo the screening procedures described previously. Once all screening procedures have commenced, research staff, along with the principal investigator, will review all relevant information and determine, based on the inclusion and exclusion criteria, if the subject is eligible to complete the remaining study procedures.

9. **Risks:** Describe the reasonably foreseeable risks, including risks to subject privacy, discomforts, or inconveniences associated with subjects participating in the research.

A medical assessment including vital signs, ECG, physical exam, routine blood tests indicating physical health and urine drug screen and pregnancy test will be completed prior to study enrollment. These safety assessments will be repeated every 2 weeks throughout the trial. Additionally, subjects will be assessed for any adverse effects of medication using the adverse events rating scale at every study visit.

The risks associated with the study include those related to: 1) screening, 2) phlebotomy, 3) Dronabinol and 4) confidentiality.

Note In previous trials involving PEA, no adverse events have been reported that have exceeded the rate observed with placebo controls. The absence of serious side effects or drugdrug interactions have been recorded is most likely due to the fact that PEA is an endogenous modulator in various foods such as eggs and milk.

1) Screening

All subjects will undergo a Structured Clinical Interview for DSM-IV conducted by a research assistant, as well as a psychiatric evaluation by the principal investigator or one of the co-investigators. The diagnostic interviews may cover issues which are stressful to a person, for example, questions regarding the experience of paranoid thoughts or social isolation.

2) Phlebotomy

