The important go/no-go decision is whether the trial, which is not a true efficacy trial but rather a Phase II pilot, provides sufficient encouragement to move forward for a Phase III trial. We propose a series of benchmarks for feasibility, tolerability and preliminary efficacy in an initial trial for go/no-go decision-making. **Feasibility**: Average treatment compliance with the Dronabinol/PEA combination of at least 80% (via pill counts and positive urine drug screen) during the trial. **Tolerability**: Attrition due to AEs of 4 or fewer subjects receiving treatment. **Safety**: Four or fewer subjects have a greater than 20% worsening of tic symptoms while in the trial. **Efficacy:** An average improvement of YGTSS severity of greater than 10% during the course of the 12-week trial.

Assuming all go/no-go decision points are met in the trial, we will additionally use the initial pilot data to design the most appropriate phase III trial design. Specifically, we will examine difference in tic severity as assessed by YGTSS (across all subjects and specifically those assigned to active medication) between week 0 (baseline) and week 12 (endpoint) to determine the time at which treatment benefits likely plateau.

SECTION VI: RESEARCH INVOLVING DRUGS, BIOLOGICS, RADIOTRACERS, PLACEBOS AND DEVICES

If this section (or one of its parts, A or B) is not applicable, state N/A and delete the rest of the section.

A. DRUGS, BIOLOGICS and RADIOTRACERS

1. **Identification of Drug, Biologic or Radiotracer:** What is (are) the **name(s)** of the drug(s) biologic(s) or radiotracer(s) being used? Identify whether FDA approval has been granted and for what indication(s).

In addition to PEA, other names of the drug include: Palmitoylethanolamide, C18H37NO2, PeaPure, Normast, Impulsin, MimyX, N-(2-hydroxyethyl)palmitate and N-palmitoylethanolamine. FDA approval has not been granted for the use of PEA. However, PEA is a primary fatty acid amine found in egg yolk. Therefore, it falls under the definition of egg yolk-derived phospholipids, which are listed on the FDA list of "Generally Recognized as Safe" with a designated number GRN No. 411. Content of PEA can also be seen under the FDA List of Indirect Additives Used in Food Contact Substances under general main term: ANIMAL OIL FATTY ACID AMIDES, Doc No. 7625, CAS RN 977139-08-4.

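### Read literally, one baseline YGTSS rating both admits subjects and anchors their change, so regression to the mean tilts the uncontrolled >10% improvement benchmark towards go

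*Combined protocol and SAP*

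**What the plan says.** **Entry.** Section V, item 7 (Inclusion/Exclusion Criteria): "Significant current tic symptoms: YGTSS total tic score greater than or equal to 22 at baseline".

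**Benchmark.** Section V, item 12 (Statistical Considerations) sets the efficacy point as "An average improvement of YGTSS severity of greater than 10% during the course of the 12-week trial". It names no reference rating.

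**Reference for change.** The next paragraph of item 12, on designing the Phase III trial, compares tic severity "between week 0 (baseline) and week 12 (endpoint) to determine the time at which treatment benefits likely plateau". This is the only reference rating named for YGTSS change.

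**Use.** "We propose a series of benchmarks for feasibility, tolerability and preliminary efficacy in an initial trial for go/no-go decision-making". Phase III design then proceeds "Assuming all go/no-go decision points are met in the trial", so the efficacy point is one of several that must all be passed.

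**Design.** Section V, item 3 describes an open-label trial in 18 adults who all receive the combination. Its schedule table has YGTSS at Screening, at Baseline and at weeks 1, 2, 4, 6, 8, 10 and 12.

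**Text pointing to Screening.** Section V, item 8 has staff review the screening information and "determine, based on the inclusion and exclusion criteria, if the subject is eligible to complete the remaining study procedures". In item 3, the table headed Baseline Assessments, which includes YGTSS, follows the paragraph that opens "Pre-study screening procedure: After an initial phone screen to rule out obvious exclusions from the study protocol".

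**The concern.** A rating scale measured with error will, by chance, read high in some people on the day they are assessed. If a threshold is applied to that reading, the admitted group contains more upward errors than downward ones. The errors are not carried forward, so the group mean drifts down at later visits even if nothing has changed. When the same reading is the starting point for change, the whole drift is counted as improvement.

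A concurrent control arm would show the same drift and cancel it. This trial has none. The drift always runs in one direction, towards passing the efficacy point, and that point feeds the decision to go to Phase III. At the threshold score of 22 the 10% margin is 0.10 × 22 = 2.2 points, so a drift of one or two points is not trivial beside it.

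**Working it through.** The plan derives no sample size, power or error rate for this benchmark, so there is no stated figure to reproduce.

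**Inputs from the plan:** threshold 22; benchmark >10%; 18 subjects; no control; separate Screening and Baseline ratings.

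**Assumptions, not in the plan:** candidate mean μ = 22, 25 or 28; SD σ = 6 or 8; retest correlation r = 0.6, 0.7, 0.8 or 0.9; normal scores; no drug or placebo effect; improvement taken as the percent change in the group mean from the reference rating to week 12.

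**Step 1. Expected fall when Baseline both qualifies and anchors.** Let a = (22 − μ)/σ and λ = φ(a)/[1 − Φ(a)].

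- Mean of admitted subjects at Baseline = μ + σλ
- Expected fall in points = (1 − r)σλ
- Expected percent fall = (1 − r)σλ / (μ + σλ)

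The chance of passing comes from simulated groups of 18.

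| μ, σ, r | λ | Baseline mean | Fall, points | Fall, % | Chance of passing >10% |
|---|---|---|---|---|---|
| 22, 8, 0.6 | 0.798 | 22 + 6.38 = 28.38 | 0.4 × 6.38 = 2.55 | 9.0 | 43% |
| 25, 8, 0.7 | 0.576 | 25 + 4.60 = 29.60 | 0.3 × 4.60 = 1.38 | 4.7 | 13% |
| 28, 6, 0.9 | 0.288 | 28 + 1.73 = 29.73 | 0.1 × 1.73 = 0.17 | 0.6 | <0.1% |

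The first and last rows are the extremes. Over all 24 combinations the fall is about 0.6–9% (median about 3%) and the chance of passing 0–43% (median about 3%). Restricting to means 22–25 and r 0.6–0.8 raises the medians to 4.6% and 10%.

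**Step 2. The other readings.** Let ρ be the correlation between the Screening and Baseline measurement errors. If one rating carries an expected selection error d = (1 − r)σλ, the other carries ρd.

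- *Screening qualifies, change from Baseline:* the bias is ρd. At ρ = 0 it is zero, and the chance of passing is at most about 6%. At ρ = 0.5 it is half of d; the fall is at most 4.7% and the chance of passing at most 19%.
- *Baseline qualifies, change from the mean of Screening and Baseline:* the bias is (1 + ρ)d/2. At ρ = 0 it is half of d (fall at most 4.7%, chance of passing at most about 15%). At ρ = 0.5 it is three quarters of d (at most 6.9% and 28%).
- *Both ratings must reach 22, change from Baseline, ρ = 0:* the fall is at most 6.2% and the chance of passing at most about 24%. Averaging the two ratings does not help here, because both are selected.

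The size therefore depends first on which rating qualifies subjects, which the plan does not settle, and then on population values that it does not give.

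**The case against.** **The literal reading is not the only one.** The eligibility section judges subjects around the screening procedures. The Baseline Assessments table includes the SCID, mental status exam and urine pregnancy test, which the schedule places at Screening and not at the Baseline visit. It also includes HAM-D and HAM-A, which the schedule starts at Baseline. So the word baseline may mean the pre-treatment work-up in general, and a Screening-based entry decision with independent errors has no expected bias. This stands as a reason to reconcile the passages. It does not remove the point: no section says that the Screening rating must reach 22, and the criterion itself says baseline.

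**The link to week 0 is inferred.** That phrase sits in the Phase III design sentence, not in the benchmark. True, but the plan offers no other reference.

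**The size is assumed, and may be small.** The plan recruits adults with significant tics who have not responded to treatment, and expects many earlier trial participants to be eligible. Both suggest candidates well above 22, where the bias shrinks. This stands, and is why mean 28 and r = 0.9 belong in the quoted range.

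**The plan disclaims efficacy.** It says that this is not a true efficacy trial, and other points must also be met, so the chance of an overall go is no higher than the chance of passing this one. That limits the consequence, but the benchmark still counts towards the decision.

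**A stronger inference to resist.** A reader might infer that selection alone would carry the trial past 10%. In no setting examined does the expected fall reach 10%. Passing with no effect needs chance variation in 18 subjects as well.

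**Conclusion.** The point holds in a limited form. Read literally, the plan uses one rating to select subjects and to anchor their change, in a trial with no control, and this biases a required decision point towards go. With no drug effect the spurious fall is about 0.6–9% (median about 3%) and the chance of passing 0–43% (median about 3%). Those figures rest wholly on the assumed mean, SD and retest correlation; the documents fix none of them.

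Two further inferences are not supported. It cannot be said that the Baseline visit definitely decides entry, because other sections allow Screening to do so. Nor should this point be stretched to the safety benchmark, "Four or fewer subjects have a greater than 20% worsening of tic symptoms while in the trial": its scale, reference rating and visit are undefined, which is a separate clarification.

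This is a modest flaw, worth correcting because the correction costs little.

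**What to change.** Do not let the same single rating qualify subjects and serve as the reference for change. Reconcile the inclusion criterion, the eligibility section, the Baseline Assessments table, the schedule and the benchmark so that each names the rating it means.

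**Preferred.** Apply the 22-point criterion to the Screening YGTSS. Define the >10% benchmark as the percent change in the group mean from the separate Baseline YGTSS to week 12, with a 95% CI. The expected bias is then about zero with independent errors, and about half remains at an error correlation of 0.5. Do not average the two ratings under this rule, because that would put the selected rating back into the reference.

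**If the criterion must stay at Baseline.** Use the mean of the Screening and Baseline ratings as the reference and show the change from Baseline alone beside it. This halves the bias with independent errors and cuts it by about a quarter at an error correlation of 0.5.

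**Cost.** Wording and one calculation; both ratings are already scheduled. Under the preferred rule some subjects will score below 22 at Baseline (about 13–29% for means 22–25 and r 0.6–0.8 with independent errors). Under the alternative the reported improvement is slightly smaller. Neither removes placebo or other non-specific improvement. For example, with a 10% non-specific improvement (mean 25, SD 7, r 0.7–0.8, Baseline qualifying), the benchmark is passed 78–83% of the time from Baseline alone and still 67–71% from the averaged reference.
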